8.0 TOXICITIES/SIDE EFFECTS

As is normally used for pediatric sedation, propofol will be used. As the length of sedation for the procedure is anticipated to be more than a few minutes, propofol will be infused using a drug infusion pump, as is routinely done now. Thus, no additional toxicities/side effects beyond those associated with the clinical administration of propofol as currently practiced are present.

9.0 PRIMARY OUTCOMES

Several factors affect the feasibility of the proposed study design, including 1) accrual rate in the proposed 4 – 6 months study period, 2) drop-out rate (children who complete the picture naming task during infusion but fail to complete the memory task post recovery), and 3) sufficient data (e.g., few observations during the picture naming task because the child falls asleep quickly; few accurate responses during the memory task).

The accrual and dropout rates will be addressed by keeping a running tally of the number of recruited participants to monitor the recruitment numbers. Our target is to recruit at least an average of 2 out of the anticipated 4 – 6 children per week. However, it would be impractical to set a fixed recruitment target for a pilot study of this nature.

Factors associated with data sufficiency will have to be determined after the data have been collected. For example, we have to wait until the data have been collected before we can begin calculating the proposed threshold statistic (Section 14 below). The statistical computer packages may or may not be able to derive a stable estimate of the threshold measure per child. This will have to be determined after each child's data have been collected, entered, and fitted for the threshold statistics.

It is premature to anticipate a statistically reliable difference between the two threshold measures, one for the *sedative* effect threshold and the other for the *memory* effect threshold. These will have to be ascertained after the data have been collected, entered, fitted, and plotted in the manner similar to Figures 1 and 2 above. It is plausible that the threshold values are similar in some children and quite different in some other children. An important goal of this study is to examine the variability between the two threshold values among the sample of children.

10.0 CRITERIA FOR REMOVAL FROM STUDY

If the patient cannot adequately perform the picture naming task (defined as verbally responding to >80% of the pictures presented before falling asleep, or half way through the list in the case of no sedation) through a significant portion of the initial 10 minute

MEMORIAL SLOAN-KETTERING CANCER CENTER IRB PROTOCOL

IRB#: 12-006A(5)

infusion, data collection will be stopped, the patient withdrawn from the study, and no further testing be performed. Similarly, if the patient is unable or unwilling to perform the recognition task, he/she will be withdrawn from the study. In the extremely unusual circumstance of severe or unanticipated toxicity from the administration of propofol (e.g. allergic reaction), the participant will be withdrawn from the study. Any participant who is removed from the study prior to the start of their procedure for reasons other than toxicity (i.e., inability or unwillingness to complete the practice or actual task) will then be administered propofol as per normal clinical practice for their procedure.

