4.2 Intervention

During induction of sedation, or in the case of no sedation, before the therapeutic procedure, children will be encouraged to name the items shown in pictures displayed, one every 5 seconds, as drug concentration is increasing. Naming pictures will ensure that items are being attended to and memory systems are engaged. The child's response will be used to assess the degree of sedation present (response present / response absent). After recovery from sedation, or after a similar time period after the therapeutic procedure

MEMORIAL SLOAN-KETTERING CANCER CENTER IRB PROTOCOL

IRB#: 12-006A(5)

(approximately 40 min) for children in the control group memory for the previously presented pictures will be tested using a yes/no response. The recognition testing set will contain both previously seen and novel items.

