Aim 2. Illustrative Examples. Aim 2 involves the calculation of a “sedation threshold” and a “memory threshold” for each child. Figures 1, and 2 provide illustrative examples on how the separate sedative and amnesic effects will be estimated statistically. An example is provided below to explain the procedures and the analytic plan.

1. “Sedation threshold”: During the 10-minute infusion of propofol, children will be presented with pictures at 5-second intervals and asked to name the picture. They will be asked to name each picture (e.g., cat, tree, pencil, etc.). A valid response is naming of the picture within 5 seconds, either correctly or incorrectly. The important response measure is whether the child is awake enough to perform the naming task. Though the picture list is a validated set of stimuli, as described in Section 7.0, some stimuli may end up being too difficult to name for children of this age group. Thus no response due to sedation may be confounded by no response due to an inappropriately difficult stimulus. Responses from the control group of children will be used to eliminate problematic stimuli which reach a given criterion of no response at both sites.

In Figures 1 and 2, the dark circles with a value of 1 on the y-axis represent that the participant is making valid responses. The dark circles with a value of 0 on the y-axis represent lack of a valid response because the participant is sedated to the point of impaired response performance as propofol concentration continues to increase. As the child gets sedated and becomes gradually sleepier as the infusion continues, he/she is less likely to make a valid response (thus the increased frequency of dark circles at the bottom of the Figures as image number increases). The dark line in Figure 1 represents the estimated sedative effects over time.

There is a vast literature in psychophysics on modeling the shapes of these curves. Since the seminal paper by Quick (1974; *Kybernetik*, 16: 65-67; PMID: 4453110), the model below has been used extensively in modeling various psychophysical functions. We will use an asymmetric Weibull cumulative density function $F(x)$ to model the overall probability of a valid response $G(x)$ over time x :

$$\begin{aligned} G(x) &= 0.5 + 0.5 \cdot F(x) \\ &= 0.5 + 0.5 \left[1 - e^{-(\alpha \cdot x)^\beta} \right], \end{aligned}$$

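### The >80% naming rule is scored during the infusion on the same responses that define sedation, so it preferentially withdraws gradually sedated children; the number lost cannot be fixed from the documents

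*Combined protocol and SAP*

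**What the plan says.** Section 10.0 defines adequate naming as "verbally responding to >80% of the pictures presented before falling asleep". For controls the check falls at a fixed point: "or half way through the list in the case of no sedation". For propofol children it is judged "through a significant portion of the initial 10 minute" infusion. A child who fails has the following consequence: "data collection will be stopped, the patient withdrawn from the study, and no further testing be performed". Neither the moment of falling asleep nor the length of the judging period is defined.

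The same response is the sedation outcome. Section 4.2: "The child's response will be used to assess the degree of sedation present (response present / response absent". Section 11.0, Aim 2: "The important response measure is whether the child is awake enough to perform the naming task". That section reads a miss as "lack of a valid response because the participant is sedated to the point of impaired response performance" and expects misses to build up: "As the child gets sedated and becomes gradually sleepier as the infusion continues, he/she is less likely to make a valid response".

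Three other places bear on the point. Section 7.0 already has a practice test with separate pictures, before any drug, and withdraws children who cannot cooperate with it. Section 9.0 leaves data sufficiency to be judged after collection and makes variation between children in the two thresholds an important goal. Section 11.0, Aim 1, asks for at least 25 of 35 propofol children with a completed recognition test and usable estimates.

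**The concern.** A rule meant to catch children who cannot do the task counts the very misses by which the study measures the drug. Excluding pictures shown after sleep onset does not cure this, because misses in the drowsy, still-awake phase remain in the count. A child who drifts off over many pictures can fail; a child who stops abruptly passes.

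A withdrawn child has no memory threshold and so cannot enter the Aim 2 comparison. The retained sample would under-represent gradual loss of response, which is part of the variation Section 9.0 wants to describe. Each withdrawal also counts against Aim 1. Section 9.0 defines drop-out as finishing naming but not the memory task, so these children fall outside that tally. The documents do not say that their naming data are analysed, do not compare them with retained children, and plan no sensitivity analysis. Controls are judged at a different point, which makes the two retained groups less comparable.

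**Working it through.** **1. The plan's own feasibility figures.** With X ~ Binomial(35, p), P(X ≥ 25) is 0.510 at p = 0.70 and 0.925 at p = 0.80. The plan states 0.51 and 0.92, so both reproduce.

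**2. How the rule selects.** Section 11.0 implies 60 pictures at encoding (half of the 120 in the recognition list). A child awake for all 60 who misses 12 while drowsy scores 48/60 = 0.80, which is not above 80%, and is withdrawn. A child who names the first 48 and then falls asleep at once scores 48/48 = 1.00 and stays. Both gave 48 responses. This step needs no simulation.

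**3. How many are lost: assumed curves.** The documents give no curve parameters for children, so everything here is illustrative. The probability of naming picture k (k = 1 to 60) is 0.95 × 0.5^((k/m)^s), where m is the child's sedation threshold and s the shape; low s means gradual loss. A child is removed if the share named before sleep onset is 0.80 or less.

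Percentage removed with m of mean 50, SD 6, and one shape for all children:

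| Sleep onset taken as | s = 4 | s = 6 | s = 8 | s = 12 |
|---|---|---|---|---|
| last valid response | 58 | 32 | 16 | 4 |
| first run of 5 misses | 48 | 26 | 15 | 5 |
| first run of 3 misses | 12 | 5 | 2 | 1 |

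Mixed cohort with m of mean 48, SD 7, and s of median 5 (log-scale SD about 0.5):

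| Rule applied | Removed | Shift in mean sedation threshold, kept minus all |
|---|---|---|
| up to last valid response | 47% | about +1.8 pictures (+1.6 to +1.9 as the spread of s varies) |
| up to first run of 5 misses | 38% | +0.4 to +0.5 |
| up to first run of 3 misses | 11% | +0.1 |
| first 30 pictures only | about 4% (3% to 6%) | +0.2 to +0.3 |

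In the first row, kept children average 49.8 against 48.0 overall, and 49.8 − 48.0 = +1.8; those removed average 46.0. Under the three sleep-onset definitions, removed children have a median shape of about 3 to 4, against about 5 to 6 in those kept.

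**4. Curves near the plan's propofol example.** Section 11.0 places that sedation threshold at image 58. With m of mean 58, SD 4 (assumed), and s from 8 to 12, about 1% to 7% are removed (extremes 0.4% and 8%).

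**5. Does the direction depend on the set-up?** Showing one picture every 5 seconds for 10 minutes gives 120 pictures rather than 60, so both counts were tried in a second model: naming probability 0.97 × exp(−ln 2 × (x/T)^b), T of mean 70% of the list and SD 15%, b of median 5. Across the two counts and three sleep-onset definitions, 4% to 56% are withdrawn: 14% to 94% of the most gradual quarter against 0% to 7% of the most abrupt. Withdrawn children have earlier mean thresholds in all six settings, by about 9 to 37 seconds.

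**6. Knock-on for Aim 1.** Suppose 80% would otherwise be usable and the rule removes a fraction w, independently of other causes. Then p = 0.80 × (1 − w).

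| w | p | P(X ≥ 25 of 35) |
|---|---|---|
| 0 | 0.80 | 0.925 |
| 5% | 0.76 | 0.80 |
| 10% | 0.72 | 0.61 |
| 25% | 0.60 | 0.11 |

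**The case against.** The rule can be read as a check of cooperation while awake, and on that reading it may remove few children. Taking sleep onset as the last valid response is the least natural definition, since one stray answer after a long silence makes the child count as awake throughout. Section 10.0 also requires the failure to extend over a substantial part of the infusion, which a single tally at sleep onset does not model. The propofol illustration in Section 3.0 shows sedation rising only at the end of the infusion, where the rule does little. All of this stands as to size. It does not remove the overlap: during the infusion nothing in the text separates poor cooperation from drug effect. The illustration comes from volunteer work, and Section 3.0 itself says children may respond differently.

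Three stronger readings are tempting but unsupported:

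- *About half the children are lost, with a bias of nearly two pictures.* The 47% and +1.8 hold only for the last-response definition in one assumed cohort.
- *The amnesia estimate is biased.* No memory threshold was simulated, and selection on the sedation curve need not carry through to the difference. Even +1.8 pictures is a tenth of the 18-picture gap (58 − 40) in the plan's example.
- *The rule makes the study look more feasible than it is.* Withdrawals lower the success count, so the error runs against declaring feasibility.

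The 0.80 in step 6 is one of the plan's two illustrative rates; its accrual argument in Section 11.0 assumes only about half of participants give adequate data. If removed children would have been unusable anyway, the fall is smaller.

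**Conclusion.** The concern holds. Followed as written, Section 10.0 selects propofol children on the sedation outcome, and gradual decliners are lost more often than abrupt ones. That direction follows from the text and appeared under every sleep-onset definition tried. It is more than a missing definition, because the withdrawal stops data collection and rules out the recognition test.

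The size is open: from about 1% of children, if responding stops late and abruptly, to about 47% in the mixed cohort under the loosest definition of sleep onset. These figures rest on assumed curve shapes, lapse rates and threshold distributions. A loss of 5% to 10% would already matter for the 25-of-35 criterion under the step 6 assumptions. The effect on the sedation-minus-memory difference remains unquantified. For a pilot this should be corrected, but it does not by itself invalidate the study.

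**What to change.** - Judge the >80% task-competence criterion on the drug-free practice set in Section 7.0. A prespecified early block is an alternative, but it is not strictly drug-free because the infusion has started. In the mixed cohort, a >80% check on the first 12 pictures removed about 2.4%.
- Do not withdraw a child for later non-responses alone. Keep all naming responses and give the recognition test to every child who is willing.
- Count children without usable estimates as failures for Aim 1.
- Define sleep onset, and report thresholds with and without the original 80% rule. Controls can keep their half-way check.

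Propofol administration, and withdrawal for toxicity or unwillingness, stay as they are. The cost is a short rewording of Section 10.0, a reporting line in Section 11.0, and some noisier or non-estimable individual curves, which Section 9.0 already plans to assess after data collection.

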11.0 BIOSTATISTICS

Overview. This study is a pilot project to separately examine the *amnesic* and the *sedative* effects of the drug propofol. The plan is to recruit a pilot sample of 40 children who will undergo sedation as part of their clinical management and give them a memory encoding task during propofol infusion to measure the effects of *sedation*. The mere task of naming a picture will encode that picture into memory. When the anesthesia has worn off (at approximately 1 hour later), children will be given a memory recognition task to measure the *amnesic* effects of propofol. We will also recruit a total of 30 children who will not undergo sedation to serve as a control group. This brings out total number of participants to 70.

Analytic Plans for the Specific Aims:

Aim 1: The primary objective is to determine the feasibility of using the visual picture naming task in pediatric patients in the clinical setting. Feasibility will be defined as, at the conclusion of the study, 25 or more of the pilot sample of 30 (control) or 35 (propofol) per group complete the recognition memory task and yield usable parameter estimates for the psychophysics function. The probability of declaring the study design feasible is 0.51 when the true population feasibility is 0.70; and the probability of a feasible study increases to 0.92 when the true population feasibility is 0.80.

Descriptive statistics will be sought to examine study feasibility. A running tally of the number of recruited participants will be kept to monitor the recruitment numbers during the anticipated 4 – 6 months study period. Due to the complex nature of this research, many factors affect study feasibility. It would be impractical and unrealistic to set an a priori feasibility target. Rather, we will monitor several factors, including patient volume, rate of study consent, the proportion of patients who can complete the experimental tasks and the practicality of fitting the psychophysical Weibul model described below. Study feasibility will be evaluated holistically at the end of the study by the study investigators.

As for the minimally sufficient number of responses, the 10-events-per-parameter rule of thumb may apply here. (34) Although that rule was developed for logistic regression, which may or may not be too restrictive for the SAS NL MIXED procedure we intend to use to fit the threshold functions.

MEMORIAL SLOAN-KETTERING CANCER CENTER IRB PROTOCOL

IRB#: 12-006A(5)

Aim 2. Illustrative Examples. Aim 2 involves the calculation of a “sedation threshold” and a “memory threshold” for each child. Figures 1, and 2 provide illustrative examples on how the separate sedative and amnesic effects will be estimated statistically. An example is provided below to explain the procedures and the analytic plan.

1. “Sedation threshold”: During the 10-minute infusion of propofol, children will be presented with pictures at 5-second intervals and asked to name the picture. They will be asked to name each picture (e.g., cat, tree, pencil, etc.). A valid response is naming of the picture within 5 seconds, either correctly or incorrectly. The important response measure is whether the child is awake enough to perform the naming task. Though the picture list is a validated set of stimuli, as described in Section 7.0, some stimuli may end up being too difficult to name for children of this age group. Thus no response due to sedation may be confounded by no response due to an inappropriately difficult stimulus. Responses from the control group of children will be used to eliminate problematic stimuli which reach a given criterion of no response at both sites.

In Figures 1 and 2, the dark circles with a value of 1 on the y-axis represent that the participant is making valid responses. The dark circles with a value of 0 on the y-axis represent lack of a valid response because the participant is sedated to the point of impaired response performance as propofol concentration continues to increase. As the child gets sedated and becomes gradually sleepier as the infusion continues, he/she is less likely to make a valid response (thus the increased frequency of dark circles at the bottom of the Figures as image number increases). The dark line in Figure 1 represents the estimated sedative effects over time.

There is a vast literature in psychophysics on modeling the shapes of these curves. Since the seminal paper by Quick (1974; *Kybernetik*, 16: 65-67; PMID: 4453110), the model below has been used extensively in modeling various psychophysical functions. We will use an asymmetric Weibull cumulative density function $F(x)$ to model the overall probability of a valid response $G(x)$ over time x :

$$\begin{aligned} G(x) &= 0.5 + 0.5 \cdot F(x) \\ &= 0.5 + 0.5 \left[1 - e^{-(\alpha \cdot x)^\beta} \right], \end{aligned}$$

where $\alpha > 0$ and $\beta > 0$ are the scale and shape parameters, respectively, and $x \geq 0$. (35) The constant of 0.5 assumes a 50-50 chance of a random response in a psychophysical task. Conventionally, the median of $F(x)$ is called the “threshold” of the underlying psychometric function (the value of x for which $F(x) = 0.5$). Because of the assumed 0.50 constant in $G(x)$, and the 0.5 times the median of the Weibull, the threshold estimate is the x value of an overall 75% response probability given the Weibull parameters. The threshold of a psychometric function generally represents the strength of stimulus that elicits a sensation or a noticeable difference. In this case the sedation threshold represents the time value of x when sedation is actuated. We will estimate one sedation curve and its corresponding threshold for each child.

MEMORIAL SLOAN-KETTERING CANCER CENTER IRB PROTOCOL

IRB#: 12-006A(5)

2. "Memory threshold": When the anesthesia has worn off at approximately 1 hour later, the child will be presented with another list of 120 pictures with half having been presented during the initial infusion of propofol. At the presentation of each picture, the child will be asked whether or not he/she remembers having seen it previously. Each response will be coded as correct (true positives and true negatives) or incorrect (false positives and false negatives). A curve may be fitted to the memory recognition data to estimate the average memory decay function for each child. In Figure 1 and 2 this is represented as the light gray curve, which can be modeled as $1 - G(x)$ above. Similarly, a threshold represents the time value (picture number) when memory fades below threshold.

The *sedation* threshold in Figure 1 is at image 25 (250 seconds), while the *memory* threshold is at approximately image 28 (280 seconds). This 30-second / 3 picture difference is taken to represent that sedation occurs concurrently with memory decay. Alternatively, in Figure 2, the *sedation* threshold is at image 58 (580 seconds) while the *memory* threshold is approximately at image 40 (400 seconds). This larger difference of 180 seconds / 18 pictures is a measure of how much sooner amnesia occurred in this instance than sedation. In this latter case, a measurable amnesic effect of 180 seconds can be inferred from the two threshold values.

Calculations of the sedation and memory thresholds. The overall statistical paradigm will involve non-linear regression modeling to estimate $G(x)$ functions for the memory and sedation curves for each child in order to address the main hypothesis:

"The threshold effect for memory will occur significantly sooner, i.e. at lower drug concentrations, than the threshold effect for sedation".

Sample Size Considerations. The proposed pilot sample of 35 children accrued to the propofol group is primarily determined by our plan to complete the study within 4-6 months. In our experience we have a pool of approximately 10 children who undergo anesthesia for clinical scans each week who would meet the eligibility criteria. Among them an anticipated 50% would agree to participate in this study. If half of these (2-3/week) produce data of sufficient quality to be able to perform curve fitting as described above, we expect to complete recruitment within 5 months.

A sample of 35 children will also yield an 80% power in a one-sample t-test against the null that the difference in the sedation and memory thresholds is zero (null $\sim N(0, 1)$), assuming a two-sided Type-I error rate of 0.05, and an alternative population distribution with a mean of 0.50 and a standard deviation of 1.0. The statistical power was estimated by the G*Power computer program.

MEMORIAL SLOAN-KETTERING CANCER CENTER IRB PROTOCOL

IRB#: 12-006A(5)

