2.0 OBJECTIVES AND SCIENTIFIC AIMS

1. The primary objective is to determine the feasibility of using the visual picture naming task in pediatric patients in the clinical setting. Feasibility will be defined as being able to accrue an average of 2 patients a week who successfully name and recognize sufficient numbers of pictures so that the thresholds for sedation and memory can be determined in each individual (as described in Section 11.0, Aim 1).
2. The strength of propofol amnesia (the effect of propofol on memory not related to sedation) will be estimated as a difference between thresholds for amnesia (loss of memory) and sedation (loss of verbal responsiveness)

MEMORIAL SLOAN-KETTERING CANCER CENTER IRB PROTOCOL

IRB#: 12-006A(5)

Hypothesis 1: The threshold effect for memory will occur significantly sooner, i.e. at lower drug concentrations, than the threshold effect for sedation, as illustrated in Fig 2 (the threshold for memory effect is illustrated by the light gray curves in the Figures, and for sedation by the dark curves).

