In summary, a rationale exists, but is not proven, for the desirability of specific amnesic properties for drugs used during sedation/anesthesia. The development of an instrument to detect the amnesic effect of a given drug in a clinical setting would not only confirm results from previous volunteer studies, but would provide an opportunity to measure an important variable in patient outcome in terms of recall of the surgical/therapeutic experience, or of patient satisfaction. If the quality of amnesia does indeed relate to outcome, then this measure applied in the clinical setting would provide a rational basis for drug selection. Future studies could be used to compare drugs with similar pharmacokinetic profiles, for example, propofol with dexmedetomidine or various inhalational agents.

A protocol using the same methodology as in the current one is now open at Boston Children's Hospital, where dexmedetomidine is used for pediatric sedation. Accrual demographics are nearly identical with the patients accrued so far to the MSKCC protocol. Inclusion of a control group at both sites will validate a more direct comparison of memory effects from propofol with those of dexmedetomidine.

MEMORIAL SLOAN-KETTERING CANCER CENTER IRB PROTOCOL

IRB#: 12-006A(5)

Post-Operative Cognitive Dysfunction

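### The printed chances of declaring feasibility (0.51 and 0.92) cover 25 of 35 propofol children only, while the rule also sets 25 of 30 controls and does not say how the groups combine

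*Combined protocol and SAP*

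**What the plan says.** The primary objective is feasibility. Section 11.0, Aim 1 defines it as "25 or more of the pilot sample of 30 (control) or 35 (propofol) per group complete the recognition memory task and yield usable parameter estimates"; the estimates meant are those of a psychophysics function that it does not name further. The next sentence reads "The probability of declaring the study design feasible is 0.51 when the true population feasibility is 0.70", and goes on to give 0.92 at a true feasibility of 0.80. Neither figure is tied to a group.

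Other statements bear on the same decision:

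- **Propofol sample.** The Overview of Section 11.0 says "The plan is to recruit a pilot sample of 40 children who will undergo sedation", which with 30 controls makes its total of 70. Aim 1 uses 35, and so does Sample Size Considerations: "The proposed pilot sample of 35 children accrued to the propofol group".
- **Whether there is a target.** The paragraph after the rule says "It would be impractical and unrealistic to set an a priori feasibility target" and leaves the judgement to the investigators, made on the whole picture when the study ends.
- **Accrual.** Section 2.0 defines feasibility as "being able to accrue an average of 2 patients a week who successfully name and recognize sufficient numbers of pictures", so that both thresholds can be found for each child, and refers to Section 11.0, Aim 1 for the detail.
- **Controls.** Section 4.1 gives them the same tasks without drug. Section 3.0 explains why they were added: "Inclusion of a control group at both sites will validate a more direct comparison of memory effects from propofol with those of dexmedetomidine".

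**The concern.** A reader will take 0.51 and 0.92 as the chance that the study is declared feasible under the rule just stated. That rule names two groups of different size and applies the same count to each, so one pair of probabilities cannot describe both. A count of 25 is a much higher bar in 30 children than in 35, and the control half of the rule has no stated probability.

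The words per group suggest a separate test in each, but nothing says whether both groups must pass, whether one is enough, or what follows if they disagree. A cut-off with stated operating characteristics also sits next to a statement that no cut-off should be set. The same results could therefore be reported as feasible or not feasible, and this is the primary objective.

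**Working it through.** **Inputs.** Cut-off 25; n = 35 propofol and n = 30 control; true rates 0.70 and 0.80; printed results 0.51 and 0.92 (all Section 11.0, Aim 1). Alternative propofol n = 40 (Section 11.0, Overview). The documents give no success rate for controls, so every control rate below is an assumption.

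**Formula.** P(X ≥ 25) for X ~ Binomial(n, p), computed exactly.

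**Step 1. Reproduce the printed pair.** With n = 35, p = 0.70 gives 0.5100 and p = 0.80 gives 0.9253. These match 0.51 and 0.92; the second looks truncated rather than rounded, which does not matter. Using n = 30, n = 40, more than 25 instead of at least 25, both groups, either group, or a pooled count of 50 of 65 or 50 of 70 does not reproduce both figures.

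**Step 2. Apply the same count to each stated size.**

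| Rule | Bar | p = 0.70 | p = 0.80 |
|---|---|---|---|
| 25 of 35 (propofol) | 25/35 = 71.4% | 0.510 | 0.925 |
| 25 of 30 (control) | 25/30 = 83.3% | 0.077 | 0.428 |
| 25 of 40 (if the Overview's number were used) | 25/40 = 62.5% | 0.885 | 0.997 |

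At higher assumed rates, controls reach 25 of 30 with probability 0.711 (rate 0.85), 0.927 (0.90) and 0.997 (0.95). They need a true rate of about 0.815 to reach 0.51 and about 0.898 to reach 0.92.

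**Step 3. Combine the groups, assuming independence.** Let a be the propofol probability and b the control probability. Both must pass: a × b. Either is enough: 1 − (1 − a)(1 − b).

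Common rate in both groups:

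- Both, 0.70: 0.5100 × 0.0766 = 0.039. Both, 0.80: 0.9253 × 0.4275 = 0.396.
- Either, 0.70: 1 − 0.4900 × 0.9234 = 0.547. Either, 0.80: 1 − 0.0747 × 0.5725 = 0.957.

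Both must pass, with propofol at 0.70 and 0.80 and controls at an assumed rate of their own:

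| Control rate | Propofol 0.70 | Propofol 0.80 |
|---|---|---|
| 0.85 (b = 0.7106) | 0.36 | 0.66 |
| 0.90 (b = 0.9268) | 0.47 | 0.86 |
| 0.95 (b = 0.9967) | 0.51 | 0.92 |

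**Step 4. Compare with Section 2.0.** Four to six months is 17.3 to 26 weeks. Twenty-five evaluable propofol children in that time is 25/17.3 = 1.4 to 25/26 = 1.0 a week. The count in Aim 1 can therefore be met while an average of 2 a week is missed, if Section 2.0 refers to propofol children. It does not say which group it covers.

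**The case against.** The strongest reply is that nothing is miscalculated. The pair matches the propofol denominator in its own sentence, and in a pilot whose investigators will weigh several factors, the cut-off may not decide alone. The first part is right, and this point should not be called an arithmetic error. The second limits the practical effect but does not remove it: the plan still prints a probability of declaring feasibility for a rule that it covers only in part.

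Several stronger readings are tempting, and the documents do not support them.

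- **The real chance is 0.04 and 0.40.** This needs both groups to be required and controls to share the propofol rate. The plan states neither. Accepting either group gives figures slightly above the printed pair at a common rate, and requiring both with controls at 0.95 leaves the pair almost unchanged.
- **The rule is bound to fail on the plan's own planning rate.** Sample Size Considerations says "If half of these (2-3/week) produce data of sufficient quality to be able to perform curve fitting as described above", and a reader might take one half as the true feasibility. That sentence is a conditional allowance for accrual time among children who agree to take part. Sections 7.0 and 10.0 withdraw children who cannot do the practice or naming task, and nothing says whether they stay in the 35. The two rates may have different denominators.
- **The rule is met automatically.** This would require the 35 to be children who already have usable data. The text speaks of children accrued and of a pilot sample, so that reading is strained.
- **Controls must yield a sedation threshold they cannot have.** The plan does not say so. Aim 1 links the recognition task with a single function, which favours a memory curve. Aim 2 uses control naming responses to remove difficult pictures, and Section 10.0 gives controls their own naming criterion. What stands is that the required function is not named, while Section 2.0 and Aim 2 speak of thresholds for each child.
- **The correct figures are those for 25 of 40.** Aim 1 pairs 25 with 35. The 40 is a conflict to reconcile, and those figures apply only if the rule changes.

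**Conclusion.** The point holds as a mis-scoped probability. The figures 0.51 and 0.92 are right for 25 of 35 propofol children and for nothing else in the rule. At the same true rates the control half has probabilities of 0.077 and 0.428.

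The effect on the overall decision cannot be fixed from the documents, because they give neither a combination rule nor a control rate. Across the cases worked above it runs from 0.039 to 0.547 where the plan prints 0.51, and from 0.396 to 0.957 where it prints 0.92. These joint figures assume independent groups. The low ends also assume a common rate, for which the documents give no basis.

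The conflicts between 35 and 40, and between a fixed cut-off and a refusal to set one, are in the text and need no assumption. This should be fixed because it governs how the primary objective is declared met.

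**What to change.** 1. Label 0.51 and 0.92 (0.925 to three decimals) as the propofol group only, 25 of 35. Reconcile 35 with 40. Recompute only if 25 of 40 becomes the rule (0.885 and 0.997).
2. State whether feasibility rests on propofol alone or on both groups. If both, print the control and joint probabilities with an assumed rate for each group; for example, controls at 0.90 with propofol at 0.70 or 0.80 gives 0.47 and 0.86. If propofol alone, report controls descriptively; the printed pair then stands once labelled.
3. Do not require a sedation threshold from undrugged controls. Score control success on completing the naming and recognition tasks.
4. Either keep the cut-off and delete the statement that no target can be set, or call 25 of 35 a descriptive benchmark for the investigators' overall judgement. Align the 2 evaluable patients a week in Section 2.0 with that choice, and say which group it covers.

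The cost is protocol wording and possibly less favourable printed probabilities. No extra patients, visits or data are needed.
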